Study Protocol and Statistical Analysis Plan NCT03854539 August 27, 2020

Protocol. Participants. Healthy male and female adult participants (ages 18+) will be recruited from the Arkansas Tech University psychology student test pool and may receive course credit for participating. Participants fill out a questionnaire screening for mental disorders and use of substances which interfere with accurate assessment of salivary alpha amylase. The questionnaire also includes items on age, ethnicity and gender. In both experiments participants will be randomly assigned to groups with stimulation order determined using a Latin square design. Protection of human subjects. The IRB protocol is under review. Women and minorities are included and their data will be analyzed in accordance with the described data analysis plan. Stimulation procedures. We will apply sham stimulation and tVNS using identical stimulation parameters with the exception of electrode placement. *Electrode Placement.* Participants in tVNS condition groups will receive stimulation via electrodes attached on the anterior and posterior ear at the concha, an area richly innervated with vagal fibers [10]. *Sham-stimulated* participants will be stimulated with identical stimulus parameters as the tVNS group with the electrodes placed on the helix region. The helix region of the ear is thought to be free of vagal or other cranial nerve fibers. *Non-stimulation* participants will receive no stimulation. In the nonstimulation condition electrodes will be applied randomly to one of the above locations without electrical stimulation. The purpose of this group is to control for the possibility that mild stimulation will increase arousal through non-vagal pathways. *Stimulation parameters.* In the first study, to establish a stimulation intensity effect curve, participants will receive 0.0, 0.25, 0.5, or 1.0mA stimulation either to the concha or helix region (sham stimulation). The stimulus will consist of trains of 30Hz, with 0.5mS pulse width. Trains will alternate 30 seconds on and 30 seconds off for five minutes. In a second study to determine the relative effects of intermittent vs constant stimulation, participants will receive helix (sham) or concha (tVNS) stimulation at the 0.5mA level. Intermittent stimulation will consist of trains of 30Hz, with 0.5mS pulse width. Trains will alternate 30 seconds on and 30 seconds off for ten minutes. Constant stimulation will be identical with the exception that instead of alternating on-off periods, the stimulation will be a single five minute on block (holds total number of impulses equal). *Salivary Alpha Amylase.* Saliva samples will be collected using the passive drool method, considered to be the superior method for collection of alpha amylase samples [11]. Participants allow drool to pool inside the oral cavity and use a straw to provide 2mL of saliva into a cryogenic sample container. Following collection samples are placed on ice and then frozen until assay. *Salivary alpha amylase assay.* Samples are assayed using kinetic reaction assay, without modifications to the manufacturer's recommended protocol (Salimetrics, State College, PA) will be used. Details on this assay can be found in Gordis *et al* [11]. For sAA, sample test volumes are 10 μ l and the lower limit of sensitivity is 0.4 U/mL. Samples are tested in duplicate with the average of the duplicates used for analysis. Duplicates exceeding 10% variance will be re-assayed. As a secondary measure, heart rate will be monitored by ECG and continuously recorded (3 lead) throughout the experiment using an iWorx TA device. Recoding electrodes are placed on the right and left clavicles and costal margin. Heart rate will be used to confirm sympathetic induction and effects of heart rate variability may later be investigated as a primary measure in future studies.

Data analysis Within-subject percent change from immediately preceding baseline scores will be calculated for each level of stimulation ([baseline/stimulation] *100). Statistical analysis of percent changes in salivary alpha amylase concentrations by stimulation group will be performed with one-way repeated measures ANOVA with Bonferroni correction for multiple comparisons of each stimulation level to the sham stimulation level. Statistical analysis to determine changes in baseline concentration of salivary alpha amylase within each intensity will be conducted using repeated measures ANOVA with Bonferroni correction for

multiple comparisons. A significance level of $p < 0.05$ will be used for all statistical tests conducted. Within-subject percent change from immediately preceding baseline scores will be calculated for each level of stimulation ($[\text{baseline}/\text{stimulation}] * 100$). Statistical analysis of percent changes in salivary alpha amylase concentrations by stimulation group will be performed with one-way repeated measures ANOVA with Bonferroni correction for multiple comparisons of each stimulation level to the sham stimulation level. Statistical analysis to determine changes in baseline concentration of salivary alpha amylase within each intensity will be conducted using repeated measures ANOVA with Bonferroni correction for multiple comparisons. A significance level of $p < 0.05$ will be used for all statistical tests conducted.

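### The Latin square controls stimulation order, but the one-way repeated measures ANOVA has no period term; adding one is cheap and gains power if the score drifts across periods

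*Combined protocol and SAP*

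**What the plan says.** The Participants section covers both experiments: "participants will be randomly assigned to groups with stimulation order determined using a Latin square design". It does not give the size or type of square, the number of periods, or the interval between conditions.

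Under Stimulation parameters, in the first study "participants will receive 0.0, 0.25, 0.5, or 1.0mA stimulation either to the concha or helix region". Under Electrode Placement, sham is helix placement: sham "participants will be stimulated with identical stimulus parameters as the tVNS group with the electrodes placed on the helix region".

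The Data analysis section takes as its outcome "Within-subject percent change from immediately preceding baseline scores", calculated at each stimulation level. The comparison by stimulation group "will be performed with one-way repeated measures ANOVA with Bonferroni correction", the correction being for "multiple comparisons of each stimulation level to the sham stimulation level". A second repeated measures ANOVA is described as "Statistical analysis to determine changes in baseline concentration of salivary alpha amylase within each intensity". Neither analysis names a period, order, sequence or carryover term.

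**The concern.** A Latin square places each condition equally often in each period, so that period variation can be separated from condition. A one-way repeated measures ANOVA removes differences between participants and fits stimulation level, and nothing else. Any period variation in the score stays in the residual.

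Scoring against the preceding baseline cancels drift that affects baseline and stimulation samples in proportion. It does not cancel a change in the response itself, such as habituation to repeated stimulation. If that occurs, the error variance is too large and a real within-subject difference is more likely to be missed. If sequences are unequally filled or conditions are missing, the contrasts also shift. The documents do not say that either will happen.

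**Working it through.** **Inputs from the documents.** Latin square order; one-way repeated measures ANOVA; significance level 0.05 with Bonferroni correction; four intensities (0.0, 0.25, 0.5, 1.0 mA) at two sites. The plan has no power figure to reproduce.

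**Assumptions.** Within-subject SD 1; true contrast of 1 SD; two-sided tests; three Bonferroni tests, so 0.05/3 = 0.0167 each; one pooled ANOVA error term; linear drift in the score with total D from first to last period. Four periods (P = 4) means the four intensities at one site with 0.0 mA as comparator. Eight (P = 8) means four intensities at two sites, all in the same participants.

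**Formulas.** With period effects p_j centred at zero:

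- Variance of a contrast: 2/n.
- Without period: error df = (n−1)(P−1), and expected error variance = 1 + n·Σp_j² / [(n−1)(P−1)].
- With period: error df = (n−1)(P−1) − (P−1), and expected error variance = 1.

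**Numbers in, n = 20, P = 4, D = 1.** The p_j are −1/2, −1/6, 1/6 and 1/2, so Σp_j² = 0.556 and n·Σp_j² = 11.11. Error df are 19 × 3 = 57 without period and 54 with it. Expected error variance without period is 1 + 11.11/57 = 1.195. For P = 8, Σp_j² = 0.857, and the expected error variance is 1 + 17.14/133 = 1.129.

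**Power**, simulated from these distributions:

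| n | Periods | Total drift | Without period | With period |
|---|---|---|---|---|
| 20 | 4 | 0.5 SD | 73.6% | 75.3% |
| 20 | 4 | 1 SD | 67.9% | 75.3% |
| 20 | 8 | 0.5 SD | 75.7% | 76.8% |
| 20 | 8 | 1 SD | 72.0% | 76.8% |
| 24 | 4 | 0.5 SD | 82.6% | 84.0% |
| 24 | 4 | 1 SD | 78.0% | 84.0% |
| 24 | 8 | 0.5 SD | 84.2% | 85.0% |
| 24 | 8 | 1 SD | 81.3% | 85.0% |

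Twenty participants cannot fill eight sequences equally; 24 fill four or eight. A direct least-squares simulation (n = 20, P = 4, D = 1; 20,000 trials) gave 68.2% and 75.7%, in agreement.

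**False positives.** At D = 1 and n = 20, the per-test error without period falls from the nominal 1.67% to 0.92% (P = 4) or 1.11% (P = 8). The test is conservative.

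**When the term does not pay.** With four periods it breaks even at a total drift of about 0.3 SD (n = 8), 0.25 SD (n = 12) and 0.15 SD (n = 20).

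**Drift that differs between people** (n = 20, P = 4). With mean drift 1 SD and person-to-person SD of 0.5 or 1, power is 65.9% against 73.1%, or 59.9% against 67.1%. The gain stays near 7 points, but the rest of the loss is not recovered. With no mean drift and person-to-person SD 1, it is 67.0% against 66.7%, so the term does not help.

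**Unequal sequences** (n = 20, P = 4, no period term). Over the 24 4×4 Latin squares with the first row fixed, counts of 6/5/5/4 shift a contrast by up to 0.07 to 0.10 SD per 1 SD of drift, depending on the square. Counts of 7/5/5/3 shift it by up to 0.13 to 0.20 SD. With period fitted the shift is 0.

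**The case against.** The strongest reply is that no error has been shown. Under balance the contrasts are unbiased, the preceding-baseline score already removes proportional drift, and baseline concentration gets its own ANOVA. The power loss needs systematic drift in the score of a size that nothing in the documents indicates. All of this stands and limits the point to an optional improvement. The baseline ANOVA may partly check stability, but it does not adjust the score.

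A second reply is that the largest gains come from the four-period case, where the comparator is 0.0 mA, whereas the plan compares with sham, defined as helix placement. References to sham, tVNS and non-stimulation participants or groups can be read as between-subject. This also stands: on that reading the figures do not describe the comparison with sham. Only the eight-period case puts helix sham within participants, and there the gain is about 1 point at 0.5 SD and 4 to 5 points at 1 SD.

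Third, the levels depend on computational choices that the plan leaves open. With separate paired t-tests (n = 20, four periods), power without period adjustment is about 70% with no drift and 63.8% at 1 SD. With seven tests instead of three (n = 20, eight periods, 1 SD), it is 60.2% without period and 66.6% with it. The levels move, but the direction does not.

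Lastly, the worked cases describe only the first study. The number of periods per participant in the second is not stated.

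**Conclusion.** The point holds as a modest one. The plan balances order and then analyses the data as if period had no effect. Under balance the only consequence is lost power, with no bias and no excess of false positives.

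Under the stated assumptions the loss is about 1 to 2 points at 0.5 SD of drift and 4 to 7.5 points at 1 SD. It disappears if drift is very small or purely individual. Sample size, SD, effect and drift are all assumed, so these figures show scale and do not predict what this trial will see. They apply only where conditions are compared within the same participants.

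**What to change.** Analyse the within-subject conditions with a mixed model: participant as random effect, stimulation condition and period as fixed effects, and the planned Bonferroni comparisons kept. A random participant intercept alone assumes equal correlation between any two conditions; the plan should say whether that is accepted.

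Also state which factors are within-subject (helix against concha in particular), the type of square, and the interval between conditions. A period term does not deal with carryover. A carryover-balanced square or a carryover sensitivity analysis is optional, since the documents do not show that carryover is present.

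**Cost.** No new data are needed, because period is known from the order list. The term uses P − 1 error df: 57 to 54 for four periods at n = 20, and 161 to 154 for eight periods at n = 24. If there is no drift, the power lost with four periods is about 0.1 point at n = 20, 0.4 to 0.5 at n = 12 and 0.8 at n = 8. With eight periods it is about 0.1, 0.2 and 0.3. The term can be added even if orders have already been run, but it should be fixed before outcomes are examined.

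### Study 1 aims to establish an intensity curve, but no planned analysis treats current as ordered or numeric, so the form of the intensity effect is neither estimated nor tested

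*Combined protocol and SAP*

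**What the plan says.** Under Stimulation parameters, the first study is introduced with its purpose: "In the first study, to establish a stimulation intensity effect curve". The currents are 0.0, 0.25, 0.5 and 1.0 mA, given at the concha or, as sham, at the helix. Sham runs at the same settings as active stimulation: "participants will be stimulated with identical stimulus parameters as the tVNS group with the electrodes placed on the helix region". On design, the Participants section says that "participants will be randomly assigned to groups with stimulation order determined using a Latin square design".

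The Data analysis section contains three steps, stated twice in the same terms:

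- A response at each level: "Within-subject percent change from immediately preceding baseline scores will be calculated for each level of stimulation".
- A main model: "Statistical analysis of percent changes in salivary alpha amylase concentrations by stimulation group will be performed with one-way repeated measures ANOVA", followed by pairwise tests "with Bonferroni correction for multiple comparisons of each stimulation level to the sham stimulation level".
- A separate repeated measures ANOVA of baseline amylase within each intensity.

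The section has no trend or polynomial contrast, regression on mA, named comparison between one current and another, or site-by-intensity term. Nor does it plan a plot, a fitted curve or confidence intervals.

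**The concern.** A curve describes how the response changes as current rises. The planned analyses treat the four currents as labels. The overall F test gives the same value if the mA labels are shuffled, so it cannot say whether the effect rises, levels off or turns down. If helix sham is one of its levels, it can also be significant because of site alone. The pairwise tests ask whether each level differs from sham, not how levels differ from one another. The third step stays within a single intensity.

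Followed exactly, the plan leaves Study 1's question without a prespecified answer. The natural substitute is to read the curve from which levels reach p<0.05. That is unsafe, because a small true effect at a low current and no effect at that current look alike in such a list.

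The gap does not depend on which sham comparator is used. With sham matched at every current, a set of level-versus-sham tests would still contain no intensity term.

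**Working it through.** **No figure to reproduce.** The documents give no sample size, power, effect size or SD. The calculation below is an illustration.

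**From the documents:** currents x = 0, 0.25, 0.5, 1.0 mA; alpha 0.05; Bonferroni correction.

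**Assumed:** n = 20, each measured at all four currents at one site; independent residuals with SD 1; two-sided tests; 0 mA as comparator; three pairwise tests, each at 0.05/3 = 0.0167; error df = 3 × (20 − 1) = 57; maximum effect 0.9 SD.

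**Linear truth** (means 0, 0.225, 0.45, 0.9 SD):

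1. Centred currents are −0.4375, −0.1875, 0.0625 and 0.5625. Their squares sum to Sxx = 0.547.
2. Trend contrast: noncentrality = 0.9 × √(20 × 0.547) = 2.98. On 57 df at 5%, power is 0.83.
3. Overall F test: noncentrality λ = 2.976² = 8.86 on 3 and 57 df. Power is 0.67.
4. Joint linear-plus-quadratic test: the same λ on 2 and 57 df. Power is 0.74.
5. Each level against 0 mA: noncentrality = difference × √(20/2), which is 0.71, 1.42 and 2.85. At 0.0167, power is 0.05, 0.16 and 0.65.
6. By simulation, at least one pair is significant in about 0.66 of runs and all three in about 0.02. Only 1.0 mA is significant in about 0.48 of runs, or roughly 73% of the runs with any significant pair.

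So under a straight line, the usual pairwise result looks like a threshold between 0.5 and 1.0 mA.

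**Other shapes, same assumptions** (power):

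| Means at the four currents (SD) | Linear trend | Joint 2-df | Overall F | Any Bonferroni pair |
|---|---|---|---|---|
| Linear: 0, 0.225, 0.45, 0.9 | 0.83 | 0.74 | 0.67 | 0.66 |
| Saturating at 0.5 mA: 0, 0.45, 0.9, 0.9 | 0.81 | 0.83 | 0.78 | 0.80 |
| Plateau from 0.25 mA: 0, 0.9, 0.9, 0.9 | 0.65 | 0.83 | 0.82 | 0.86 |
| Inverted U: 0, 0.45, 0.9, 0.45 | 0.27 | 0.68 | 0.63 | 0.67 |

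For the joint test, λ is the sum of the squared linear and quadratic noncentralities. For the inverted U this is 1.361² + 2.433² = 7.77.

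**Concha-minus-helix curve.** With equal, independent error at each site, the variance doubles. For the linear shape the trend noncentrality falls to 2.976/√2 = 2.10. Power is 0.54 with 20 participants measured at both sites (57 df) and 0.55 with 20 in each site group (114 df). With 10 per group the noncentrality is 2.105/√2 = 1.49, and power is 0.31. The joint test of the same contrast, with λ = 2.105² = 4.43 on 2 and 57 df, has power 0.43.

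**Two separate 5% contrasts.** If either the linear or the quadratic contrast sufficed, the false-positive rate would be about 1 − 0.95² = 0.0975. Simulation with the shared error term gives about 0.096. One joint test keeps it at 0.05.

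**The case against.** A reader might infer that the plan never tests whether the response depends on intensity and yields no estimate at all. The documents do not support that. The one-way repeated measures ANOVA carries an overall F test across levels, which is a real, though unordered, test of dependence on stimulation level. Percent change is calculated at each level, so the level means could be plotted against mA as a descriptive curve. The documents do not define the curve as a fitted slope, and they do not say it will be read from which levels are significant. With only three nonzero currents, choosing level means over a parametric contrast is partly a matter of preference.

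A second tempting inference is that a trend test is simply more powerful than what is planned. That holds for a linear response. For saturation the gain over the F test is small (0.81 against 0.78). For a plateau and an inverted U the linear contrast is clearly worse.

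These objections limit the point but do not remove it. The F test cannot give direction, slope or shape. A plot of means is neither planned nor accompanied by any interval or test. The weakness of a linear contrast alone is a reason to test linear and quadratic terms together.

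One practical objection also stands. Site may be between participants, and the electrodes in the non-stimulation condition go to one location at random. A within-person concha-minus-helix difference may therefore not exist at every current, and the analysis has to be a model that allows for this.

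**Conclusion.** The point holds in this form: the plan has an unordered overall test and level-versus-sham comparisons, but nothing that estimates or tests the form of the intensity effect that Study 1 sets out to establish. This follows from the text and does not depend on the assumed numbers, nor on whether currents are given within or between participants.

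The size is illustrative only. Under the stated one-site assumptions and a linear response, an apparent threshold at 1.0 mA arises in about 48% of runs. The trend test has power 0.83 against 0.67 for the F test. For the vagus-specific contrast the trend power is about 0.54, so the one-site gain should not be promised for it. The omission should be corrected before analysis. It does not invalidate the tests already planned.

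**What to change.** Add to the Data analysis section, for Study 1:

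- A repeated measures or mixed model with site (concha, helix), intensity (0, 0.25, 0.5, 1.0 mA at actual spacing) and their interaction. Site is entered within or between participants as the design dictates, and the text should say which applies.
- One joint 2-df linear-plus-quadratic test at 5% for the intensity relation. For the vagus-specific curve, it is applied to the site-by-intensity contrasts.
- Slope, curvature and fitted level means, each with 95% confidence intervals.
- A statement that the curve will not be inferred from which levels are individually significant.

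Keep the overall ANOVA and the level-versus-sham comparisons as follow-up.

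The cost is a few more lines of analysis text and no new data. The joint test gives up some power against a single linear contrast when the response is truly linear (0.74 against 0.83 in the one-site illustration). In return it holds up for the saturating, plateau and inverted-U shapes.

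### The protocol describes electrode site as a grouping of participants, but the planned one-way repeated measures ANOVA needs a sham score from every participant

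*Combined protocol and SAP*

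**What the plan says.** All places are in the Combined protocol and SAP.

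- **Protocol, Participants:** "In both experiments participants will be randomly assigned to groups with stimulation order determined using a Latin square design". The factor that is ordered is not named, nor is the number of stimulations per person.
- **Protocol, Electrode Placement:** "Participants in tVNS condition groups will receive stimulation via electrodes attached on the anterior and posterior ear at the concha". Of the sham arm it says that these "participants will be stimulated with identical stimulus parameters as the tVNS group with the electrodes placed on the helix region". Of the third arm it says that these "participants will receive no stimulation". The next sentence speaks of a condition instead: "In the nonstimulation condition electrodes will be applied randomly to one of the above locations without electrical stimulation". The sentence after that calls it a group again.
- **Protocol, Stimulation parameters:** in Study 1, "participants will receive 0.0, 0.25, 0.5, or 1.0mA stimulation either to the concha or helix region (sham stimulation"). In Study 2, "participants will receive helix (sham) or concha (tVNS) stimulation at the 0.5mA level", given as intermittent or constant stimulation.
- **Data analysis:** the outcome is each person's percent change from the baseline sample taken before each level. The test is a "one-way repeated measures ANOVA with Bonferroni correction for multiple comparisons of each stimulation level to the sham stimulation level". The factor in that model is itself called a stimulation group.

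**The concern.** A one-way repeated measures ANOVA compares levels that were all measured in the same people, so a contrast of each level with sham needs a sham score from each person. The protocol's wording on site points the other way: people are placed in a tVNS group, a sham group or a no-stimulation group. These are two stated rules that do not fit together, not merely a missing detail.

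Two things are at stake. Staff who follow the protocol's group wording could give each person one site only, and the sham scores that the analysis expects would never be collected. An analyst who then follows the Data analysis section would have to treat different people as repeated measurements of one person, in the contrast that separates stimulation at the vagal site from the same current elsewhere on the ear.

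**Working it through.** The documents give no sample size, standard deviation or correlation for this comparison, so there is no planned figure to reproduce. The check is whether each design that the text allows can support the planned test.

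**Step 1. Designs the text allows (Study 1)**

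| Design | Does a tVNS participant have a sham score? | Does the planned test work as written? |
|---|---|---|
| A. Site and intensity both between participants | No | No; the Latin square would also have nothing to order |
| B. Site between, intensity within | No | No; site needs a between-participant factor |
| C. Intensity between, site within | Yes, at that person's intensity | No; the levels lie in different people, so one one-way model across levels fails |
| D. Every participant receives both sites and all levels | Yes | Yes |

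B satisfies both halves of the allocation sentence (assignment to groups, and an order within each person). D is what the planned analysis needs, but it fits least well with the group wording and with the either/or choice of site. The same reasoning applies to Study 2, with pattern (intermittent or constant) in place of intensity.

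**Step 2. Precision if site is between participants**

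Inputs: n scores per condition; common variance s² of the change scores; within-person correlation r, assumed to lie between 0.3 and 0.7 (not given in the documents).

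- Paired contrast: variance = 2s²(1 − r)/n
- Independent groups of n: variance = 2s²/n
- Ratio of standard errors = 1/√(1 − r)
- r = 0.3: 1/√0.7 = 1.20
- r = 0.7: 1/√0.3 = 1.83

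The ratio holds n per condition fixed, so the between-participant design also uses twice as many people for that contrast.

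**Step 3. Does that ratio measure the error of the planned test?**

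Suppose site is between participants and unrelated people are entered as one subject. The expected error mean square of the one-way repeated measures model is the average variance minus the average covariance over pairs of levels, s²(1 − f·r), where f is the share of level pairs that come from the same person. The true variance of a concha-helix difference is still 2s²/n. The ratio of true to reported standard error is therefore 1/√(1 − f·r).

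- One level from each person: f = 0, ratio 1.00.
- Three levels from each of two people: f = 6/15 = 0.40, ratio 1/√0.88 = 1.07 at r = 0.3 and 1/√0.72 = 1.18 at r = 0.7.
- Four levels from each: f = 12/28 = 0.43, ratio 1.07 and 1.20.
- Three concha levels from one person and one sham level from another: f = 3/6 = 0.50, ratio 1/√0.85 = 1.08 and 1/√0.65 = 1.24.

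So the misapplied test would understate the standard error by a factor of 1.00 to about 1.24 in these layouts. The full 1.20 to 1.83 would arise only if a purely within-person error term were applied to a between-person site contrast.

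**The case against.** The strongest reply is that the study is a crossover described in loose language. A Latin square order makes sense only if each person receives more than one stimulation, and site may be among the things ordered. The Data analysis section treats sham as one stimulation level with its own baseline, and it uses the word group for the levels of a repeated measures model, so that word need not mean separate people. No stimulation is both a condition and the 0.0 mA level of the intensity series. The either/or wording does not settle the matter, since the same sentence lists the intensities with an or as well.

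Much of this stands. A reader might infer that tVNS participants are definitely scheduled without a sham session. The documents do not support that, because they contain no per-participant schedule and a within-person reading remains open. The conflict survives all the same: nothing in the protocol says that a participant receives both sites, and only design D lets the planned test run as written.

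Two other inferences should be resisted. A reader might take sham to be the only control for non-vagal effects, but the protocol gives the no-stimulation group the purpose of guarding against arousal by non-vagal routes. A reader might also take 1.20 to 1.83 as the amount by which the planned test understates its standard error; Step 3 of the working shows that it is not.

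**Conclusion.** The concern holds as a conflict between the allocation wording and the analysis model. Under the literal reading of the protocol the planned test cannot validly make the sham comparison. It is valid as written only if each participant receives sham and all levels, and that is not stated. Which design is intended cannot be decided from the documents.

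The size depends on that choice. If site is within participants with all levels, correcting the wording resolves the matter and no precision is lost. If site is between participants, the sham contrast is less precise than a paired one by the factor in Step 2. That rests on an assumed r of 0.3 to 0.7, equal variances and equal n per condition. The point should be settled before data are collected, because sham sessions that were never held cannot be recovered by analysis.

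**What to change.** Reconcile the Protocol and Data analysis sections. For each study, state:

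1. what a group is;
2. which conditions (site, intensity including 0.0 mA, and pattern) each participant receives;
3. which factor the Latin square orders.

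Then match the model to that statement:

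- **Site within participants:** keep a repeated measures analysis, and use wording for conditions instead of groups throughout.
- **Site between participants:** replace the one-way repeated measures ANOVA with a mixed model (site between; intensity in Study 1 or pattern in Study 2 within). Test concha against helix with between-participant error, and reserve the within-participant error term for contrasts within a site. If no stimulation is also a separate set of people, treat it in the same way.

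This review does not say which allocation or stimulation schedule is right; that is for the sponsor to state. The cost is a few sentences of protocol and analysis text if the intended allocation is only being made explicit. If site is between participants, the price is the less precise sham contrast, which the sponsor should allow for when setting the number of participants.

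### Study 2 asks how intermittent and constant stimulation compare, but the analysis plan names no contrast between them

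*Combined protocol and SAP*

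**What the plan says.** Under Stimulation parameters, the protocol introduces the second experiment with one purpose: "In a second study to determine the relative effects of intermittent vs constant stimulation". Intensity is fixed and site varies: "participants will receive helix (sham) or concha (tVNS) stimulation at the 0.5mA level". The intermittent pattern alternates 30 seconds on and 30 seconds off over ten minutes. For the constant pattern, "instead of alternating on-off periods, the stimulation will be a single five minute on block (holds total number of impulses equal").

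On sham, Stimulation procedures says: "We will apply sham stimulation and tVNS using identical stimulation parameters with the exception of electrode placement". On layout, Participants says: "In both experiments participants will be randomly assigned to groups with stimulation order determined using a Latin square design".

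The Data analysis section is one paragraph, printed twice, and names two analyses:

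- "Statistical analysis of percent changes in salivary alpha amylase concentrations by stimulation group will be performed with one-way repeated measures ANOVA". The only follow-ups that it names here, adjusted by Bonferroni, are "multiple comparisons of each stimulation level to the sham stimulation level".
- A repeated measures ANOVA of "changes in baseline concentration of salivary alpha amylase within each intensity", also with Bonferroni correction.

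All tests use a 0.05 significance level. Neither copy of the paragraph mentions intermittent stimulation, constant stimulation or a pattern factor.

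**The concern.** Both analyses are worded for the intensity curve of Study 1. Study 2 has one intensity, so an analysis organised by intensity gives it nothing to compare, and that analysis concerns baseline values in any case. What remains is a set of comparisons with sham. The plan therefore does not say which estimate or p-value answers Study 2's question.

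Two things are at stake. First, the route that the plan names invites the conclusion that the patterns differ because one is significant against sham and the other is not. That can happen by chance when they work equally well. Second, a direct concha contrast, a site-by-pattern interaction and a pair of sham comparisons answer different questions and can disagree. With none named, the choice can be made after the data are seen.

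**Working it through.** **Aim against analysis**

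| Study 2 needs | Data analysis section offers |
|---|---|
| Intermittent versus constant, percent change | One-way omnibus test across stimulation groups |
| A named contrast with an estimate | Follow-up comparisons with sham only |
| Separation of site (concha, helix) from pattern | A one-way model, which does not separate them |
| One intensity, 0.5 mA | Baseline analysis organised by intensity |

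The plan states no sample size, SD, effect size or power, so there is no such figure to reproduce. Its equal-impulse statement does check out: ten minutes at half on-time is 300 s, and 300 s × 30 Hz = 9,000; the constant block is also 300 s × 30 Hz = 9,000.

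**How often the sham comparisons disagree when the patterns are equal**

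Assume that each sham comparison has power p and that the two correlate at r. Then P(exactly one significant) = 2(p − P11), where P11 is the probability that both are significant, from the bivariate normal.

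| r | p = 80% | p = 50% |
|---|---|---|
| 0 | 2(0.800 − 0.640) = 32% | 2(0.500 − 0.250) = 50% |
| 0.3 | 27% | 40% |
| 0.5 | 2(0.800 − 0.687) = 23% | 2(0.500 − 0.333) = 33% |
| 0.7 | 17% | 25% |

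These rates depend on the power per comparison, so they are the same at a 0.05 or a Bonferroni 0.025 threshold.

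The value of r follows from the layout. Let ρ be the within-person correlation, with equal variances and equal correlations (compound symmetry):

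- Four within-person cells, each pattern with its own sham: r = 0.
- One shared sham, everything within person: r = (1 − ρ)/(2(1 − ρ)) = 0.5.
- Separate shams, site between persons and pattern within: r = ρ.
- One shared sham, site between persons and pattern within: r = (1 + ρ)/2, so 0.75 at ρ = 0.5, giving 16% and 23%.

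**What the missing contrast would cost in power**

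Suppose that intermittent has 80% power against sham, and let f be the constant effect divided by the intermittent effect. At two-sided 0.05 the noncentrality against sham is d = 1.960 + 0.842 = 2.802. The interaction is the difference of the two sham comparisons, so its noncentrality is d(1 − f)/√(2(1 − r)). It is tested at two-sided 0.05.

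| Contrast and layout | f = 0 | f = 0.5 |
|---|---|---|
| Interaction, four within-person cells (r = 0) | 2.802/1.414 = 1.981, power 51% | 0.991, power 17% |
| Interaction, site between, ρ = 0.3 | 66% | 22% |
| Interaction, site between, ρ = 0.5 | 80% | 29% |
| Interaction, site between, ρ = 0.7 | 95% | 44% |
| Direct concha contrast, all within person | 2.802, power 80% | 1.401, power 29% |

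If the 80% refers to a Bonferroni 0.025 threshold, d = 3.083. The four-cell interaction then has 59% (f = 0) or 19% (f = 0.5), and the direct contrast 87% or 34%.

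**The case against.** The best reply is that the ANOVA by stimulation group could take intermittent and constant as groups, so its omnibus test would respond to a difference between them. That stands: a reader might infer that the patterns cannot enter the planned analysis at all, and the text does not support that. The reply still does not supply the missing test. A significant omnibus result could come entirely from active versus sham, and the only follow-ups named for that ANOVA go to sham. The Bonferroni comparisons in the second analysis are not identified and concern baseline values.

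A second reply is that every rate above is hypothetical and depends on layout. That also stands. A reader might take 32% or 50% as the expected rate of discordant results, or 51% and 17% as the general power of the interaction. The documents support neither, because both sets need uncorrelated sham comparisons. The protocol speaks of tVNS groups and sham-stimulated participants, and of random assignment to groups with Latin-square order, so site between persons with pattern within is as natural a reading as any. There the discordance is lower and the interaction stronger.

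Third, the protocol already discloses the ten- and five-minute lengths and its reason for them. It is no contradiction that pattern and session length move together. It limits what the result can be said to show.

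**Conclusion.** The concern holds on the text alone: Study 2's one stated question has no pre-specified contrast, and nothing elsewhere in the document supplies one. This should be settled before Study 2 data are analysed.

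The size is illustrative. With equal true effects and assumed power of 80% or 50% per sham comparison, discordant results arise 32% or 50% of the time at zero correlation, 23% or 33% at correlation 0.5, and less often above that. Which figure applies cannot be settled from the documents, because they do not say which factors are within persons or whether helix sham is given in both patterns. No figure printed in the plan is shown to be wrong by this point.

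**What to change.** In the Data analysis section, name one primary Study 2 contrast, with its estimate, 95% CI and two-sided 0.05 test. State which factors are within and which between persons, and whether helix sham is given in both patterns. Then:

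- **Helix sham in both patterns**, as the identical-parameters sentence implies: use the site-by-pattern interaction, (concha minus helix, intermittent) minus (concha minus helix, constant). It removes drift common to both sites.
- **One sham condition:** use concha-intermittent versus concha-constant directly. State that drift arising from the ten- versus five-minute lengths is not removed.

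Compute the contrast on a correctly oriented percent change. The printed formula divides baseline by the stimulation value, so it falls as amylase rises and would reverse the sign of the estimate. In either case, state that the result reflects pattern and session length together at 9,000 impulses each.

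The cost is a few sentences and no new condition. The downside is precision: as the power table shows, the interaction can be much weaker than the sham comparison with four within-person cells, and as strong or stronger if site is between persons and ρ is 0.5 or more. Since the documents state no sample size, there is none to check against; the report should give the precision that the chosen contrast achieves.
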